### 4.2 Endpoints

#### 4.2.1 Primary Endpoint

- Postoperative cTnI

#### 4.2.2 Secondary Endpoints

- Serum creatinine
- Urinary MALDI-MS

#### 4.2.3 Other Clinical Outcomes Collected

- Nadir haemoglobin (first 7 days following admission)
- Haemoglobin(Hb) at time of surgery
- Perioperative blood loss
- Number of units transfused
- Blood transfusion rate

- Haemoglobin concentration at blood transfusion
- 30-day major adverse cardiac events
- Myocardial Infarction within 30 days (using universal definition)
- MINS within 30 days
- Mortality (30; 90 days)
- POMS score
- Hospital length of stay
- Unplanned hospital readmission within 90 days
- HRQoL at 90 days
- Secondary care costs during 90 days post-randomisation

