#### 4.1.2 Secondary Objectives

- To estimate the rate of acute kidney injury using Acute Kidney Injury Network (AKIN) Classification, Serum Creatinine and Urinary MALDI-MS.
- To observe whether changes in Troponin I levels are reflected by electrocardiographic changes via an ECG taken on the 3rd postoperative day.
- To define the clinical diagnosis rate of myocardial infarction according to universal definitions
- To observe rate of transfusion and transfusion trigger
- To estimate the incidence of postoperative complications, in particular infectious complications and delirium.
- To measure hospital length of stay
- To measure 30-day, 90-day and hospital mortality.
- To measure economic and quality of life outcomes

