## 5. Study Design

This will be a prospective cohort study. Patients will be consented and then enrolled in the study within 48 hours of hospital admission with fractured neck of femur. Over the intra- and postoperative period, we will collect baseline demographic data, and daily information regarding myocardial infarction, postoperative complications (including death) and blood transfusion.

We will take blood samples for markers of renal and kidney injury preoperatively and at 24 hours and 72 hours following surgery. We will record the results of blood tests that have been routinely taken. Patients will have a point-of-care haemoglobin measurement immediately following surgery in recovery using the “haemocue” system. Urine will be collected at 2 time points post-operatively (within 24 hours and 4-6 days post-operatively).

We will perform a postoperative ECG 72 hours following surgery. We will collect clinical data on postoperative morbidity score (POMS) on day 7, on infectious and cardiac complications prior to hospital discharge. We will also collect economic and quality of life data for up to 90 days following surgery.

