## 10. Follow up

Patients will be prospectively followed up until hospital discharge by the research team. Hospital records will be checked for hospital mortality by the research team. The research team will access hospital/primary care records for up to 90 days to capture data regarding cardiac events and mortality.

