### 11.2 Data Analysis

We will report main trial outcomes by anaemic and non anaemic groups. Continuous data will be presented as mean (95% CI), or median (IQR) if non-normally distributed. Binary data will be presented as frequency (%). Parametric and non parametric variables will be compared using appropriate statistical tests.

Exploratory analyses will utilize the hsTnI profiles to define the optimum method for defining myocardial injury in a subsequent trial, for example maximum values, AUC analyses, and proportions exceeding threshold values. Comparisons across the two study groups will be used to explore the possible validity of this measure in a subsequent large transfusion trigger trial, specifically whether differences exist between patients with different haemoglobin profiles during the perioperative period. Other analyses will explore the relative associations between markers of kidney injury, anaemia, and other factors using regression analysis. We will report the proportion of eligible patients, Hb concentration distribution between groups and mean red blood cell use across groups with 95% confident intervals (CI).

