### **12. Trial management and oversight arrangements**

This study will be run in coordination with the Edinburgh Clinical Trials Unit (ECTU).

As this is a purely observational study the likelihood of adverse events is low however we will use ECTU protocols for audit and monitoring.

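### Secondary care costs are timed from a randomisation that this cohort study does not have, and skewed costs would be reported without a mean or confidence interval

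*Combined protocol and SAP*

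**What the plan says.** The outcome lists in sections 3.2 and 4.2.3 carry the same item: "Secondary care costs during 90 days post-randomisation". Section 5 describes the design differently: "This will be a prospective cohort study". Section 12 agrees, in the sentence beginning "As this is a purely observational study the likelihood of adverse events is low".

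Section 5 also gives a time frame for the economic data: "We will also collect economic and quality of life data for up to 90 days following surgery". Section 8 lists secondary care costs under its 90-day heading without saying 90 days from what. Section 10 says "The research team will access hospital/primary care records for up to 90 days to capture data regarding cardiac events and mortality", which again gives no starting point and does not mention costs.

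Economic outcomes are a stated secondary objective in section 4.1.2: "To measure economic and quality of life outcomes". No unit costs, cost estimand or cost distribution is given. The only summary rule that applies to costs is the general one in section 11.2: "Continuous data will be presented as mean (95% CI), or median (IQR) if non-normally distributed".

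**The concern.** There are two separate problems.

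**Start of the window.** Both outcome definitions refer to an event that never happens. Section 5 supplies a different anchor, surgery, so the document disagrees with itself. Admission, enrolment and surgery can fall on different days, and two analysts working from the same records could cost different periods.

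**Summary measure.** The rule in section 11.2 withdraws the mean and its interval exactly when the data are not normal. For costs the mean is the quantity of interest, because mean cost times number of patients is total cost; no such identity holds for the median. Section 11.1 says that the study's outcome estimates will be used to design a full trial, and section 2.5 says that the wider programme aims at cost-effective use of blood. A median and IQR alone would not supply the mean cost, or its precision, for that purpose.

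**Working it through.** The plan states no cost figure, so there is none to reproduce. The check has three parts.

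**1. Start of the window, section by section**

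| Section | Start of the 90 days |
|---|---|
| 3.2 and 4.2.3 | Randomisation (does not occur) |
| 5 | Surgery |
| 8, 90-day list | Not stated |
| 10 | Not stated; names cardiac events and mortality only |

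Enrolment is a further possible origin: "Patients will be consented and then enrolled in the study within 48 hours of hospital admission with fractured neck of femur". Section 8 collects the date of admission, the date of surgery and the length of stay, so either admission or surgery could be used without new data. Section 5 does not say whether costs from the index stay before surgery are counted.

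**2. Median against mean**

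Inputs: the rule in 11.2 (from the plan), and a cost distribution (not in the plan, so assumed).

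- Lognormal: mean = exp(μ + σ²/2), median = exp(μ) and σ² = ln(1 + CV²), where CV is the coefficient of variation. So median/mean = exp(−σ²/2) = 1/√(1 + CV²).
- Gamma: with shape k = 1/CV², median/mean = (50th percentile of a unit-scale gamma with shape k)/k.

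| Assumed CV | Lognormal median/mean | Gamma median/mean |
|---|---|---|
| 0.25 | 0.97 | 0.98 |
| 0.5 | 1/√1.25 = 0.89 | 0.92 |
| 1 | 1/√2 = 0.71 | 0.69 |
| 1.5 | 1/√3.25 = 0.55 | 0.41 |
| 2 | 1/√5 = 0.45 | 0.17 |

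Over this grid the median lies about 2% to 83% below the mean, depending wholly on the assumed shape and spread. The direction depends on skew: for a left-skewed variable (Weibull, shape 5) median/mean is 1.01.

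On scaling: with 200 patients, total cost is 200 × mean. At a lognormal CV of 1, 200 × median = 200 × 0.71 × mean, or about 141 × mean (using 0.707). The product is therefore not the cohort's total cost.

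**3. Precision of a mean at the planned size**

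With complete data, the approximate 95% half-width relative to the mean is 1.96 × CV/√n.

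- All 200 patients: 1.96/√200 = 0.139, giving about ±7%, ±14% and ±28% at CV 0.5, 1 and 2.
- One anaemia group of 100 (section 11.1 expects half to be anaemic): 1.96/√100 = 0.196, giving about ±10%, ±20% and ±39%.

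**The case against.** The strongest reply is that little is at stake. Costs are the last item among the other clinical outcomes of an exploratory study with no power calculation. No cost-effectiveness model or budget-impact analysis is planned here; the reference to cost-effectiveness in section 2.5 concerns a later trial. Patient-level data stay in the study database, so a mean can be computed afterwards. All of this stands, and it keeps the point minor. It does not make the outcome definition correct or add the mean to the report.

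Four stronger readings are tempting but not supported:

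- *The economic data have no start date.* Section 5 gives one, surgery. The defect is a conflicting origin, not a missing one.
- *The plan understates average cost by some percentage.* A median correctly summarises a different quantity, and the plan does not propose to present it as the mean. The 11.2 rule is conditional on non-normality, and no cost distribution is given, so no percentage can be attributed to this study.
- *Preoperative bed-days are excluded.* Section 5 is silent on this, and the dates needed to recover those days are collected.
- *Units transfused need the same exemption.* Section 11.2 already commits to mean red cell use by group with 95% intervals, so that request is largely met.

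It is also fair to say that a bootstrap interval and a rule for deaths are refinements whose absence is not in itself an error in an exploratory plan.

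**Conclusion.** Both parts hold, at minor severity. The randomisation wording in 3.2 and 4.2.3 is wrong for this design and disagrees with section 5; this follows from the text alone. The reporting gap also follows from the text: if costs are not normally distributed, section 11.2 yields no mean and no confidence interval for them.

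That the median would fall below the mean rests on an assumption of right skew, which is usual for costs but not documented here. The size of the gap is unknown. The range of 0.89 to 0.45 for a lognormal CV of 0.5 to 2 is illustration, not a property of the study. No clinical outcome or main comparison is affected.

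**What to change.** 1. In 3.2 and 4.2.3, replace the reference to randomisation with one origin that agrees with section 5, and use the same origin in sections 8 and 10.
2. State whether preoperative days of the index stay are counted. Counting from surgery gives every patient the same nominal 90 days. Counting from admission to 90 days after surgery captures the whole index stay, but the window then varies with the wait for surgery. Either is workable if written down.
3. In 11.2, add that secondary care costs will be reported as the arithmetic mean with a bootstrap 95% CI, overall and by anaemia group, whatever the skew, with median (IQR) as a supplement.
4. Keep patients who die before day 90 in the analysis at their accrued cost.

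The cost is a few sentences of wording and no new data collection. The downside is that the interval around a skewed mean may be wide with 200 patients, and wider within each anaemia group. That width is itself useful to those designing the later trial.

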## 5. Study Design

This will be a prospective cohort study. Patients will be consented and then enrolled in the study within 48 hours of hospital admission with fractured neck of femur. Over the intra- and postoperative period, we will collect baseline demographic data, and daily information regarding myocardial infarction, postoperative complications (including death) and blood transfusion.

We will take blood samples for markers of renal and kidney injury preoperatively and at 24 hours and 72 hours following surgery. We will record the results of blood tests that have been routinely taken. Patients will have a point-of-care haemoglobin measurement immediately following surgery in recovery using the “haemocue” system. Urine will be collected at 2 time points post-operatively (within 24 hours and 4-6 days post-operatively).

We will perform a postoperative ECG 72 hours following surgery. We will collect clinical data on postoperative morbidity score (POMS) on day 7, on infectious and cardiac complications prior to hospital discharge. We will also collect economic and quality of life data for up to 90 days following surgery.

## 6. Study population

Patients aged over 50 years having emergency surgery for fracture neck of femur at the Royal Infirmary Edinburgh.

### 6.1 Recruitment Rate

The trauma and orthopaedic unit at the Royal Infirmary of Edinburgh perform over 1000 procedures for fractured neck of femur per year and 98% undergo surgical fixation. Based on

published data(12) and UK audit data we expect ≈60% (N = 600) of patients to have cardiovascular co-morbidity. Assuming a recruitment rate of 50%, 300 patients would be potentially recruited in 12 months (7 per week). Assuming a “worst case scenario” of 30% recruitment, we expect to recruit ≈200 patients over 12 months.

## **6.2 Inclusion Criteria**

- Patients with fractured neck of femur.
- Age over 50 years
- Within 48 hours of presentation to the emergency department
- Patients who have consented to take part in the study

## **6.3 Exclusion Criteria**

- Age under 50 years
- Refusal of consent

# **7. Participant Selection and Enrolment**

## **7.1 Identifying participants**

Patients will be identified in the emergency department, on orthopaedic wards or from operating lists. The research team will approach the potential participant or their next of kin (if patient lacks capacity) either in person or by telephone to discuss involvement in the study. If interested in participating, the appropriate information sheet will be provided and a maximum of 24 hours will be given to consider the study and ask any questions. If interested, consent will be sought for inclusion in the study.

## **7.2 Consent**

### **7.2.1 Obtaining Consent from participants**

Patients who are deemed capable of consent by the clinician in charge will be given a patient information leaflet to read which will fully explain the study with its risks and benefits. This will then be discussed with them and consent will be sought by the chief investigator or appropriately trained member of the team.

### **7.2.2 Consent in the case of incapacity**

For most patients admitted to hospital, the case notes have clear information relating to the identity of the guardian/welfare attorney/nearest relative. Contact details for a first contact (and additional contacts) are usually documented in the unitary patient record (a key

document in the patient's medical notes), and/or in the Emergency Department sheet. The patient's guardian/welfare attorney/nearest relative will be identified from this information. No incapacitated patient will be entered into the study without consent from a guardian, welfare attorney or relative. We shall approach the guardian/welfare attorney/nearest relative during a visit to the hospital. He/she will be informed of the nature of the study and given an information sheet and consent form. Should the guardian/welfare attorney/nearest relative consider giving informed consent, he/she will be asked to sign the consent form. Direct consent of these individuals will be preferable, however witnessed phone consent will be acceptable, with the individual signing the consent form at the earliest opportunity. In such cases where telephone consent is obtained, a verbal description of the study will be provided, with an opportunity to ask any questions. This process will be witnessed by a member of the clinical team who is not connected with the study.

### **7.3 Ineligible and non-recruited participants**

A screening log will be maintained of patients eligible but not recruited to the study and the reasons for this.

## **8. Data Collection**

All data will be entered directly onto a secure, trial specific database using REDCap: Research Electronic Data Capture (Vanderbilt University, USA). This is a secure, password protected platform, hosted on University of Edinburgh servers. All identifiable data will be removed before the dataset is extracted for analysis.

The following data will be collected from all participants recruited onto the study:

### *Preoperative Data*

At baseline the following information will be collected:

- date of admission
- Demographic information
- Type of surgery proposed
- Cardiovascular risk factors
- Cardiac medications
- Charleson Comorbidity Index
- Preoperative haemoglobin (Hb)
- Preoperative serum TnI
- Preoperative Creatinine

- Preoperative Urinary MALDI-MS

*Intraoperative Data*

- Date of surgery
- Type of anaesthesia
- Duration of surgery
- Lowest intraoperative Haematocrit (Hct) or Hb measured
- Hb immediately after surgery
- Number of units blood transfused
- Postoperative analgesia
- Postoperative destination (e.g. Ward, Critical Care Unit)

*Postoperative Data*

First 72 hours postop

- Serum TnI and Creatinine, Hb, urinary MALDI-MS within 24 hours and 4-6 days postoperatively. Where possible blood samples will be timed with existing blood sampling.
- ECG on the 3rd postoperative day
- Transfusion requirement
- Relevant clinical information major adverse cardiac events (MACE) including myocardial infarction.

Hospital Discharge/30 days

- Transfusion requirement
- Length of hospital stay
- MACE
- POMS
- Incidence of Delirium
- Infectious complications
- Mortality 30 days

90 Days

- Emergency readmission
- Mortality
- HRQoL
- Secondary care costs

## 9. Subgroups

### 9.1 Anaemia

We will explore cardiac and renal biomarker changes in patients with and without anaemia according to WHO definition and also by current transfusion guidelines. We hope this will inform a study looking at myocardial injury as an endpoint for restrictive versus liberal blood transfusion practice for patients with cardiovascular disease in intensive care. This will enable us to study the range of Troponin values that might occur when the patient becomes eligible for entry to this with a preoperative haemoglobin of 90g/l or less. We will also be able to look at Troponin I levels pre- and post-transfusion. This will not require any further blood samples.

## 10. Follow up

Patients will be prospectively followed up until hospital discharge by the research team. Hospital records will be checked for hospital mortality by the research team. The research team will access hospital/primary care records for up to 90 days to capture data regarding cardiac events and mortality.

## 11. Statistics and Data Analysis

### 11.1 Power

We plan to recruit 200 patients. This is an exploratory study, and not based on a formal power calculation. We propose to recruit for fixed period of 12 months to establish recruitment rates, and provide estimates of the values and distribution of clinical outcomes that will be used to design a full trial. On the admission figures quoted above, 600 patients would be eligible for recruitment each year. Assuming a 50% refusal rate, we could realistically expect to recruit 300 (95% Confidence Intervals [CI] 280-320). Planned recruitment of 200 is well within these limits. We expect 50% of participants to be anaemic, based on previous work. (10)

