### 3.2 PICO Design

Study design was developed using “Patient Intervention Comparator Outcome” (PICO) method.

**Population:** We will recruit 200 adult patients undergoing emergency surgery for fractured neck of femur, aged over 50 years.

**Intervention:** We will use blood samples taken preoperatively and at 24 and 72 hours by the research team or (where able) leftover serum from routinely collected blood samples to minimise need for venepuncture in these patients. We will perform an ECG on the third postoperative day. Urine will be collected at 2 time points post-operatively (within 24 hours and 4-6 days post-operatively).

**Comparator:** This is an exploratory study in which we are trying to understand the dynamics of serum Troponin I, serum creatinine and urinary MALDI-MS following surgery. We will compare patterns of cardiac and renal injury in anaemic and non-anaemic patients.

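### The recruitment forecast in sections 6.1 and 11.1 gives 600 two meanings and misstates the 30% yield, the weekly rate and where 200 lies against 280-320 (minor)

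*Combined protocol and SAP*

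**What the plan says.** Section 6.1 (Recruitment Rate) starts from a unit said to "perform over 1000 procedures for fractured neck of femur per year and 98% undergo surgical fixation". It then expects about 60%, printed as N = 600, "of patients to have cardiovascular co-morbidity". At 50% uptake, "300 patients would be potentially recruited in 12 months (7 per week" is the forecast. For the worst case it gives "30% recruitment, we expect to recruit ≈200 patients over 12 months".

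Section 11.1 (Power) refers back to those admission figures and says that "600 patients would be eligible for recruitment each year". After 50% refusal it expects to "recruit 300 (95% Confidence Intervals [CI] 280-320). Planned recruitment of 200 is well within these limits". The same section says that the target of 200 does not come from a formal power calculation, and adds: "We propose to recruit for fixed period of 12 months to establish recruitment rates".

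Section 3.2 describes the sample as follows: "We will recruit 200 adult patients undergoing emergency surgery for fractured neck of femur, aged over 50 years". Sections 6, 6.2 and 6.3 set entry by the fracture, emergency surgery, age over 50, presentation within 48 hours, and consent. None of them asks for cardiovascular disease, and the lay summary (1.2) opens the study to every patient who comes to the hospital with a broken hip.

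**The concern.** One number carries two meanings. In 6.1 the 600 counts patients with cardiovascular disease; in 11.1 it counts patients eligible for the study, although eligibility does not depend on cardiovascular disease. Three further figures do not follow from the base of 600: the worst-case yield, the weekly rate, and the claim that 200 lies inside the forecast interval.

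These figures are the only support offered for reaching 200 in the fixed period. Section 11.1 also makes recruitment rates something the study is meant to establish for a later trial. An observed rate cannot be compared sensibly with a forecast whose denominator is a different population.

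**Working it through.** **Inputs.** From 6.1: 1,000 procedures a year (the text says over 1,000, so this is a round figure), 98% surgical, 60% with cardiovascular disease, 50% and 30% uptake. From 11.1: base 600, forecast 300, interval 280-320, target 200, 12 months.

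**What reproduces.**
- 0.60 × 1,000 = 600. The 600 is therefore the cardiovascular subset.
- 0.50 × 600 = 300, as stated.
- Binomial 95% range at n = 600, p = 0.5: 300 ± 1.96 × √(600 × 0.5 × 0.5) = 300 ± 1.96 × 12.25 = 276 to 324. The printed 280-320 is close to this (it matches the 90% range, 279.9 to 320.1). I make no separate point of the difference.

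**What does not reproduce.**
- *Worst case.* 0.30 × 600 = 180, not ≈200. Applying the 98% first gives 0.30 × 588 = 176. A yield of 200 at 30% needs 200 / 0.30 = 667 patients in the base, or 667 / 0.60 = about 1,111 procedures.
- *Weekly rate.* 300 / 52 = 5.8. A 50-week year gives 6.0 and a 48-week year 6.25; none of these gives 7. Seven per week is 7 × 52 = 364 a year, or 364 / 600 = 61% uptake, against the stated 50%.
- *Position of 200.* 280 − 200 = 80. The target is 80 below the lower limit.

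**The same forecast on each possible base.** The all-patient figures are upper figures on the round 1,000, because the documents do not say how many patients the age and 48-hour limits remove.

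| Base | 50% uptake | 30% uptake | Uptake needed for 200 |
|---|---|---|---|
| 600 (cardiovascular subset) | 300 (5.8 per week) | 180 (3.5 per week) | 200 / 600 = 33% |
| 980 (0.98 × 1,000, all surgical patients) | 490 (9.4 per week) | 294 (5.7 per week) | 200 / 980 = 20% |

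At 30% uptake, 200 is missed only if fewer than about 667 patients are eligible. From 980, that means losing more than 980 − 667 = 313 patients, or 32%.

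**What the interval covers.** It describes chance variation with uptake fixed at 50%. It carries no uncertainty about the 50% itself: the plan's own 30% scenario, 180 on this base, lies far outside 280-320.

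**The case against.** The best reply is that the practical conclusion survives. If 600 is the wrong base, the right one is larger and the error is conservative: about 294 patients at 30% uptake, before losses, is well above 200. The shortfall to 180 exists only on the base that the entry criteria contradict, so the two errors cannot both do harm. This stands, and it sets the severity.

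Second, 6.1 is written in approximations (over 1,000, ≈60%, ≈200), and the sentence about the limits probably meant that 200 sits comfortably below an expected 300. That is a plausible reading of intent. But N = 600 is printed and 300 is computed from it; the same base cannot give 300 at 50% and 200 at 30%. The sentence about the limits is false as it stands.

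Third, 600 may have been chosen as a cautious base. Neither section says so, and 11.1 calls it the eligible number.

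Fourth, little depends on these figures. The sample size is not power-based. As an illustration, for a 40% troponin-release proportion (the upper figure in section 1.1), the 95% half-width is about 6.8 percentage points with 200 patients and 7.2 with 180. The screening log (7.3) and the reported proportion of eligible patients (11.2) will let an observed recruitment rate be derived. This also stands.

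A reader might infer that the study is likely to miss its target, or that it was meant to enrol only patients with cardiovascular disease. The documents support neither. The first needs 600 to be the true pool, or losses of about a third that no section reports. The second conflicts with sections 1.2, 3.2, 6, 6.2 and 6.3.

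**Conclusion.** Wrong as written, and minor. The 600 is the cardiovascular subset in 6.1 and the eligible number in 11.1. On that printed base the worst case is 180 (20 short of the target), the weekly rate at 50% is 5.8, and 200 is outside the quoted interval. These results are direct arithmetic on the stated inputs.

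The consequence depends on which base the sponsor intends. If it is 600, the plan's own worst case falls short of 200. If it is everyone who meets 6.2 and 6.3, 200 in 12 months remains feasible at 30% uptake unless losses leave fewer than about 667 eligible. The figure of 980 rests on applying 98% to a round 1,000 and deducts nothing for the age and 48-hour limits.

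**What to change.** Use one named denominator in both 6.1 and 11.1.

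- **If it is all patients meeting 6.2 and 6.3:** give about 980 surgical patients a year, before age and 48-hour losses, and say that those losses are not known. Restate the yields as upper figures of about 490 at 50% (9.4 per week) and about 294 at 30% (5.7 per week). Say that 200 needs at least about 20% uptake.
- **If 600 is kept as a deliberately conservative base:** say so, and stop calling it the eligible number. Restate the worst case as 180, below the target, and the weekly rate at 50% as 5.8. Say that 200 needs about 33% uptake.

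In either case, replace the sentence that places 200 within the limits with one saying that 200 is below the expected yield and giving the uptake it requires on the chosen base. Label any interval that is kept as binomial variation at the assumed 50% only, and note that it does not cover the 30% scenario.

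The cost is a text edit in two sections, with no added patients, data items or procedures. If 600 is kept, the protocol has to acknowledge that its worst case does not reach 200.
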